4.3 Baseline practice, practice staff and patient characteristics

Baseline practice and practice staff characteristics include:

- State (Victoria, Tasmania)
- IRSD terciles based on the Index of Relative Socio-Economic Disadvantage (IRSD) ¹⁰ using the practice postcode. The first tercile represents relatively disadvantaged sociodemographic geographic areas compared to geographic areas with higher ranks (Tercile 3).
- Practice participation in a formalized QI program in the past 6 months (yes, no)
- Practice size based on the GP full-time equivalent (FTE) of 4 or less FTE or greater than 4 FTE as reported by the practice. FTE will be defined as the total number of full-time GPs plus the total number of part time GPs multiplied by 0.5FTE.
- GPs sex (male, female)
- GPs age group (<35 years; 35 to 50 years; >50 years)
- Number of FTE registered nurses. FTE will be defined as the total number of full-time nurses plus the total number of part time nurses multiplied by 0.5FTE.
- Registered nurses' sex (male, female)
- Registered nurses age group (<35 years; 35 to 50 years; >50 years)
- Number of FTE practice managers and administrative staff. FTE will be defined as the total number of full-time practice managers/administrative staff plus the total number of part time practice managers/administrative staff multiplied by 0.5FTE.
- Practice managers/administrative staff sex (male, female)
- Practice managers/administrative staff age group (<35 years; 35 to 50 years; >50 years)

Patient characteristics and pathology tests, medications prescribed, referrals and observations recorded at baseline (4th October 2021) for the closed cohort and at time of entry into the study for the open cohort, that will be extracted from the EMR include:

- Age (years)
- Sex (male, female, other)

- Hb (g/L)
- MCH (fL)
- MCV (pg)
- Ferritin (μg/L)
- Platelets (UI/ml)
- PSA (ng/ml)
- Free to total PSA (%)
- Recorded diagnosis of relevant cancer in the 5 years prior to baseline (yes/no)

Other information extracted from the EMR that occur during the trial period:

- Pregnancy
- Patient deceased

4.4 Analysis methods

4.4.1 Withdrawal/follow-up

Staff within practices and/or the practice may withdraw from the study. If a practice withdraws, then no further patient data will be extracted from the EMR system. However, existing data (prior to notice of withdrawal) will be used in the final analysis unless the practice requests existing data also be excluded. Individual patients can also withdraw their data by notifying their general practice that they no longer consent to their data being used for research purposes. As the intervention is applied at the general practice level within the EMR system this means that no further patient data will be extracted. However, existing data (prior to notice of withdrawal) will be used in the final analysis unless the participant requests existing data also be excluded.

4.4.2 Descriptive analysis

The flow of practices and eligible patients from recruitment to trial end will be shown in a CONSORT diagram,¹ see Appendix A for the template. The report will include the number of practices approached for involvement in the trial, the number of eligible practices, the number of practices consented, the number of eligible practices randomised by their study arm, together with the total number and the mean number of eligible patients per practice and number that were included in the intention to treat analysis. The number of practices and/or patients who withdraw or discontinue will also be summarised by study arm and period that the withdrawal/discontinuation occurred (0-6 months, 7-9 months, 10-12 months). When such information is available, the reason a practice withdrew or discontinued the intervention will be reported by study arm.

Descriptive statistics will be used to describe general practice and patients' baseline characteristics and baseline outcome measures overall and by study arm as outlined in Appendix B Table 1 and Table 2. Descriptive statistics will also be used to summarise other information extracted from the EMR that occur during the trial period by study arm, for the closed and open cohort separately and overall. Categorical data will be summarised using counts and percentages, according to the number of eligible patients with available data. Continuous data will be summarised using arithmetic mean, standard deviation if the data have a symmetric distribution. When appropriate, continuous outcome data with a right skewed distribution may be presented as a geometric mean instead of an arithmetic mean. Otherwise, if the distribution if the data is non-symmetrical, the median and interquartile range (25th and 75th percentiles) will be presented instead. The intra-cluster correlation coefficient with 95%

intervals will also be reported for baseline patient measurements estimated using one-way analysis of variance.

4.4.3 Primary analysis

The primary analysis will use an intention to treat (ITT) approach, where all practices randomised will be included in the analysis by their allocated study arm status, regardless of whether they received all, part or none of the intended intervention.

4.4.4 Primary outcome

For the primary outcome, the odds ratio (relative measure) and the difference in proportions between the intervention and control arms (absolute measure) will be estimated using a generalised linear model (GLM) with the logit link and identity link functions, respectively, and binomial distribution for both models. Both models will include randomisation stratification factors, GP FTE and IRSD terciles as covariates, and use Generalised Estimating Equations with an exchangeable correlation structure and robust standard errors to allow for correlation of outcomes within general practice. If the model used to estimate the risk difference fails to converge, the risk difference will be derived from the GLM with the logit link function.^{11,12}

The absolute (difference in proportions between the intervention and control arms) and relative (odds ratio) estimated intervention effects for the primary outcome will be reported with 95% confidence intervals and p-values.

4.4.5 Secondary outcomes analysis

Statistical methods described in the primary outcome will be used for the **binary secondary outcomes 1-5.**

Secondary outcome 6 will utilise a Poisson mixed effects model (or a Negative Binomial mixed effects model if overdispersion is detected), with fixed effects for study arm and the randomisation stratification factors (GP FTE and IRSD terciles), and random effect for general practice. The estimated intervention effect will be reported as differences in rate between the intervention and control arms and rate ratios with 95% confidence intervals and p-values.

Secondary outcome 7 will be analysed using a time to event analysis to compare the time to investigation for patients in the open cohort with an altered test results identified as at risk of an undiagnosed cancer between the study arms using a Cox proportional hazards model, adjusted for the randomisation stratification factors (GP FTE and IRSD terciles). Robust standard errors will be used to adjust for clustering effect by general practice. The proportional hazards assumption will be assessed following a two-step procedure: (1) calculate covariate specific tests and (2) plot the scaled and smoothed scaled Schoenfeld residuals obtained from the model.¹³ Kaplan-Meier survival curves will also be used to present time to event by study arm¹⁴, and the overall survival data will be summarised following a stratified proportional hazards model or a parametric model as appropriate.¹³ A sensitivity analysis using a competing risk analysis will be considered if patients at risk of undiagnosed cancer have died prior to an investigation/end of the trial follow-up period.

Estimates of the intervention effect will be reported as hazard ratios and 95% confidence intervals and p-value.

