4.1 Primary outcome

The **primary outcome** is the proportion of eligible patients identified as at risk of undiagnosed prostate, oesophageal, gastric, colorectal, endometrial, lung or ovarian cancer that have been assessed and investigated according to NICE², Cancer Council Victoria⁴, Victorian Government Department of Health and Human Services⁸, Prostate Cancer Foundation of Australia guidelines⁵, within the 12-month trial period. The absence of any relevant recorded investigation, prescription, observation, or diagnosis during the trial period will be considered equivalent to the patient not being assessed or investigated.

The primary outcome will include any relevant investigation, dependent on whether patients were identified as at risk of cancer for iron deficiency anaemia, raised platelets or raised PSA. The relevant investigation must occur between being identified as at risk of an undiagnosed cancer (either at baseline or within the following 6 months), and the trial end date (30th Sept 2022).

For each patient identified as at risk of cancer with one or more markers of anaemia, a relevant investigation includes a repeat full blood count, iron studies, coeliac disease serology, FOBT, transvaginal ultrasound, referral to gastroenterologist, assessment of upper or lower GI symptoms and/or haematuria, prescription of an oral supplement and/or record of an iron infusion.

For each patient identified as at risk of cancer with a raised platelet count, a relevant investigation includes a repeat platelet count, chest x-ray, chest CT, FOBT, CA-125, transvaginal ultrasound, assessment for symptoms for lung, colorectal, gastro-oesophageal, ovarian or endometrial cancer, referral to a gastroenterologist, respiratory physician, or gynaecologist.

For each patient identified at risk of cancer with a raised PSA, a relevant investigation includes a repeat PSA test, free to total PSA percentage and/or referral to a urologist.

For any patient identified as at risk of cancer with more than one altered test result (e.g., anaemia and raised platelets), we will consider a relevant investigation from either marker as the equivalent of being assessed and investigated according to guidelines. In usual care, it is expected that the GP would prioritise care or use a sequential manner in responding to multiple possible investigations.

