- (4) Proportion of eligible patients whose sex at birth is coded as male in the EMR in the closed and open cohort with one raised PSA that have been followed up according to Cancer Council Australia guidelines⁴ within the 12-month trial period. Relevant investigations include a repeat PSA test, free to total PSA percentage and/or referral to a urologist^{5,8}. The absence of any of relevant recorded investigation during the trial period will be considered equivalent to not being investigated.
- (5) Proportion of eligible patients in the closed and open cohorts that have a new recorded diagnosis of prostate, oesophageal, gastric, colorectal, endometrial, lung or ovarian cancer recorded in the general practice EMR within the 12-month trial period. The absence of any of recorded diagnosis during the trial period will be considered equivalent of no diagnosis being made.
- (6) The rate of general practice encounters per eligible patient over the 12-month trial period. This will be calculated using total number of general practice visits over the trial period of all eligible patients identified as at risk of an undiagnosed cancer in the closed cohort divided by the total time they were observed in the trial. For each patient, time will be calculated from the date the trial commenced (4th Oct 2021) to the end of the trial (30th September 2022). If the patient enters in the open cohort, the time observed will be calculated from the date they the trial to the end of the trial (30th September 2022). For patients/practices that discontinue during the trial period, time observed will be calculated from they entered the (namely, the 4th October 2021 for the closed cohort or date they first report of an abnormal test result for the open cohort) to the date the patient(s) discontinued/withdrew from the trial.

(7) Time to investigation for patients with abnormal pathology results identified as at risk of an undiagnosed cancer in the open cohort. This includes any investigation, treatment, review of symptoms or referrals as described in the primary outcome. Time to investigation will be defined as the number of days between the initial altered test result date and the first investigation (retesting, investigations, treatments, referrals and review of symptoms). Outcomes will be assessed at 12 months from baseline and patient records without follow-up action by this time will be censored.

Health economics outcomes are:

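### The Cox model for time to investigation (cancer-risk outcome 7) should stratify its baseline hazard by entry marker; without that, the hazard ratio may be attenuated and some power lost

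*SAP*

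**What the plan says.** All references are to the cancer-risk SAP.

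- **Population.** Section 4.2, outcome 7, is "Time to investigation for patients with abnormal pathology results identified as at risk of an undiagnosed cancer in the open cohort". All three markers are taken together.
- **Event and time origin.** "Time to investigation will be defined as the number of days between the initial altered test result date and the first investigation". What counts is carried over from the primary outcome: "This includes any investigation, treatment, review of symptoms or referrals as described in the primary outcome". Section 4.1 makes that list "dependent on whether patients were identified as at risk of cancer for iron deficiency anaemia, raised platelets or raised PSA".
- **Model.** Section 4.4.5 compares the arms "using a Cox proportional hazards model, adjusted for the randomisation stratification factors (GP FTE and IRSD terciles"), and adds: "Robust standard errors will be used to adjust for clustering effect by general practice".
- **Checks and alternatives.** "The proportional hazards assumption will be assessed following a two-step procedure". The same paragraph says that "the overall survival data will be summarised following a stratified proportional hazards model or a parametric model as appropriate". It names no stratifying variable and no condition for using that model.
- **Extra covariates.** Sensitivity analysis 1 (section 4.5.1) adds earlier QI participation, age, sex and open or closed cohort. Entry marker is not among them, and the cohort term is constant in an outcome that uses the open cohort only.

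**The concern.** The event is the first action from a list, and the list differs by marker. Section 4.1 gives nine kinds of action for anaemia: five tests, a gastroenterology referral, symptom assessment, an oral supplement and an iron infusion. It gives ten for raised platelets (six tests, symptom assessment and three kinds of referral) and three for raised PSA. A patient with more than one altered result can be counted through either list. It is therefore plausible that the time to the first qualifying action differs between markers.

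If it does, and the program speeds up action by the same factor within each marker, a model with one baseline hazard does not return that factor. Patients with the quickly actioned marker leave the risk set first, and sooner in the better arm. The patients still at risk in that arm are then increasingly those with slow markers, and the pooled hazard ratio falls below the within-marker value.

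What is at stake is precision and the size of the estimate on the only time-to-event outcome in the plan. Entry marker is known for every patient from the eligibility rules in section 2.2, so the information that would prevent the loss is already at hand.

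**Working it through.** The SAP states no event count, power, marker mix or expected hazard ratio for outcome 7, so there is no planned figure to reproduce. The check asks what the planned model estimates when the within-marker effect is constant.

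**Inputs from the SAP**

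- Open-cohort entry from 4 October 2021 to 4 April 2022 (section 2.2), 182 days.
- Follow-up ends on 30 September 2022 (section 2.6), so each patient has 179 to 361 days.
- 1:1 allocation (section 2); two-sided p-values and 95% intervals (section 3.1).

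**Assumed inputs**

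- Marker mix w = 72/13/15% for anaemia/platelets/PSA.
- Constant hazards within marker, uniform entry, true within-marker hazard ratio θ = 1.25.
- Proportion p actioned by day 180 in the control arm: mild spread 75/65/55%, strong spread 85/60/45%, or equal.
- Clustering and the practice-level factors are left out.

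**Step 1: hazards.** λ = −ln(1 − p)/180 per day.

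- Mild: 0.00770, 0.00583, 0.00444.
- Strong: 0.01054, 0.00509, 0.00332.

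**Step 2: what the pooled model estimates.** Let G(t) be the chance of still being under follow-up at day t: 1 up to day 179, then falling linearly to 0 at day 361. For arm a (0 control, 1 program):

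- at risk: A_a(t) = G(t) Σ w exp(−θ^a λ t)
- events: e_a(t) = G(t) Σ w θ^a λ exp(−θ^a λ t)

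The pooled log hazard ratio β solves

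∫ { e_1 − (e_0 + e_1) · A_1 exp(β) / [A_1 exp(β) + A_0] } dt = 0.

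**Step 3: results for θ = 1.25**

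| Spread | Pooled HR | Share of log HR lost |
|---|---|---|
| Equal hazards | 1.250 | 0 |
| Mild, 75/65/55% | 1.242 | 1 − ln 1.2421/ln 1.25 = 1 − 0.2168/0.2231 = 2.8% |
| Strong, 85/60/45% | 1.214 | 1 − ln 1.2144/ln 1.25 = 1 − 0.1943/0.2231 = 12.9% |

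With θ = 1 the pooled value is exactly 1, whatever the spread.

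**Step 4: power.** Take a design with 80% power for the within-marker effect and hold the standard error fixed. Power becomes Φ(2.802 × share kept − 1.960).

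- Mild: 2.802 × 0.972 − 1.960 = 0.763, so about 78%.
- Strong: 2.802 × 0.871 − 1.960 = 0.480, so about 68%.

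**Step 5: does stratifying recover the effect?** A separate simulation used 60 runs of 3,000 patients, a 50/25/25% mix and θ = 1.50. Here the assumed control proportions are those actioned by 12 months.

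| Anaemia/platelets/PSA | Pooled HR | Stratified by marker |
|---|---|---|
| 75/60/40% | 1.474 | 1.514 |
| 90/70/40% | 1.414 | 1.496 |
| 95/60/30% | 1.351 | 1.500 |

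The Monte Carlo error of the pooled log hazard ratio is about 0.006. Stratifying returns 1.50 within simulation error. Entering marker as a covariate gave nearly the same values (1.513, 1.496, 1.501).

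**Step 6: sensitivity.** Solving the equation in step 2 for θ = 1.50 over three assumed mixes (70/20/10, 50/25/25, equal thirds), again with 12-month proportions, gives a log-HR loss of:

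- 1–2% for 70/65/50%
- 3.5–5.6% for 75/60/40%
- 10–15% for 90/70/40%

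Weibull shapes of 0.6 and 1.5 in place of constant hazards changed little: with the 50/25/25% mix, 1.405–1.419 for the 90/70/40% case and 1.463–1.469 for the 75/60/40% case.

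**The case against.** **The premise is not documented.** This stands. A reader might infer from the lists that speed must differ strongly by marker. The SAP gives no marker-specific rates, and one routine repeat test is enough for every marker. The number of list items is a poor guide to speed: platelets has about as many as anaemia, yet the strong-spread scenario puts them far apart. Unequal speeds are likely, not established, and with equal speeds nothing is lost.

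**Nothing is invalid.** This also stands. A reader might infer an inflated error rate or a biased test. The null value is preserved, and the pooled hazard ratio is a legitimate marginal quantity. Chance differences between practices in marker mix are covered by randomisation and practice-robust standard errors. Adjusting only for the randomisation factors is the SAP's consistent choice.

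**The proportional-hazards check.** A reader might infer that the marker mix alone would trip this check and push the analysis to another model. At trial size it rarely would. Under the strong spread the pooled hazard ratio is 1.2453 over the first 30 days and 1.1767 after day 90, a log difference of 0.057. In an assumed trial of 1,600 patients that difference has a standard error of about 0.13 to 0.14 before clustering. A rough two-window test would then reject about 7% of the time against a nominal 5%, and about 5% under the mild spread. Nor does section 4.4.5 make any alternative model conditional on the check.

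**Partial cover elsewhere.** Age and sex in sensitivity analysis 1 are partial proxies, since PSA entry is male only and age limits differ. But men also enter through anaemia and platelets. Outcomes 1, 3 and 4 look at follow-up marker by marker, but not at time. The stratified-model option in section 4.4.5 names no stratum, so it leaves the choice open.

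**Conclusion.** The plan fits one baseline hazard to patients whose event definition depends on their entry marker, and the marker enters no model and no named stratum. If speed differs by marker and the program works, the reported hazard ratio is attenuated and some power is lost. Under the assumed 72/13/15% mix and a within-marker hazard ratio of 1.25, the loss on the log scale runs from 0 (equal hazards) through about 3% (mild spread) to about 13% (strong spread). Losses of 10% or more need large gaps between markers. The direction follows from the model; the size rests wholly on assumed mix and speeds. This is an efficiency improvement to a secondary outcome, worth making because it is nearly free. It is not an error of validity.

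**What to change.** In section 4.4.5 of the cancer-risk SAP:

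- Stratify the baseline hazard of the outcome 7 Cox model by entry marker: anaemia, platelets, PSA, more than one.
- Define the stratum only by results on the date of the patient's first qualifying altered test. Later tests must not change it, because repeat testing is itself part of the outcome.
- Keep a common arm effect, GP FTE and IRSD terciles as covariates, and practice-robust standard errors.
- Run the proportional-hazards check for arm on this stratified model.

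The cost is one SAP sentence and one option in the model call; no new data are needed. Two consequences should be stated. No hazard ratio for the markers themselves is estimated, which the SAP does not ask for. The arm hazard ratio becomes conditional on marker and should be reported as such.

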4.4.6 Health economic outcomes

Costs of the installation of the software program and training of the general practice staff to use the software (**Outcome 8**) will be summarised using descriptive statistics.

Health care service costs (**Outcome 9**) will be compared between the intervention and control arms using a GLM with a log link and gamma distribution, two-part model or mixtures model depending on the distribution of costs.

4.5 Supplementary analyses

4.5.1 Sensitivity analyses 1: Adjustment of additional covariates

Sensitivity analysis of primary and secondary outcomes will additionally adjust for four confounders measured at baseline: prior practice participation in a formalised quality improvement program (yes, no), patient's' age at entry into the cohort, sex (male, female, other) and whether they were identified in the open or closed cohort. These variables will be added as covariates to the regression models described for the primary analysis.

4.5.2 Sensitivity analysis 2: Intercurrent events

All eligible patients will be included in the primary ITT analysis, including any patients who die during the trial period. Patients who become pregnant during the trial will also be included in the ITT analysis, as the clinical management of this sub-group of patients should not change. We expect the numbers who die over the 12 months of the trial period or become pregnant to be less than 10% of the sample size and similar in the two arms. However, if they do exceed 10% of the sample size, we will conduct a sensitivity analysis for the primary outcome excluding these patients from the ITT analysis.

